6.2.6. Visit 7, Day 85/Week 12 (±3 days)

- Administer PROs including PtGA, DLQI, EQ-5D-5L, HADS, and POEM;
- Obtain weight;
- Obtain pre-dose vital signs including pulse rate, sitting blood pressure, respiratory rate and oral or tympanic temperature (after at least 5 minutes of rest);
- Review PSAAD daily completion (in selected countries). ruritus NRS completion for this visit in the eDiary;
- Review any changes in the subject's concomitant medications and treatments information:
- Check subject understanding of protocol guidance for the use of background topical therapy as described in Section 5.9.1, ensure subject adherence to background topical therapy requirements and re-educate as required;
- Conduct targeted physical examination;
- Conduct clinical evaluations including IGA, SCORAD, EASI and BSA (calculated in the EASI);
- Perform a single 12-lead electrocardiogram (ECG);
- Obtain samples for laboratory testing: serum chemistry, hematology (including coagulation panel), CCI , and urinalysis;

C

- For China, Republic of Korea, Taiwan, and Japan only: For subjects who had HBV DNA testing at Screening, collect blood sample for repeat HBV DNA testing, as appropriate;
- Urine pregnancy test (female subjects of childbearing potential). A negative urine pregnancy test must be obtained prior to dosing with the investigational product;
- Assess need for contraception and adherence to applicable lifestyle requirements (Section 4.4). Establish willingness and ability to comply with lifestyle requirements going forward in the study;
- Review eDiary to assess completion;
- Perform drug accountability procedures;
- Dispense oral investigational product to the subject;

- Administer oral investigational product and observe dosing;
- Dispense injectable investigational product to the subject;
- Unblinded administrator/trainer: observe the administration of injectable investigational product performed by the subject or his/her caregiver;
- Assess and record any Adverse Events since the last visit.

6.2.7. Visit 8, Day 113/Week 16 (±3 days)

- Administer PROs including PtGA, DLQI, EQ-5D-5L, CCI HADS, and POEM;
- Obtain pre-dose vital signs including pulse rate, sitting blood pressure, respiratory rate and oral or tympanic temperature (after at least 5 minutes of rest);
- Review PSAAD daily completion (in selected countries), Pruritus NRS completion for this visit in the eDiary;
- Review any changes in the subject's concomitant medication and treatments information;
- Check subject understanding of protocol guidance for the use of background topical therapy as described in Section 5.9.1, ensure subject adherence to background topical therapy requirements and re-educate as required;
- Conduct targeted physical examination;
- Conduct clinical evaluations including IGA, SCORAD, EASI and BSA (calculated in the EASI);
- Perform a single 12-lead electrocardiogram (ECG);
- Obtain samples for laboratory testing: serum chemistry, hematology (including coagulation panel), lipid profile (fasting), and urinalysis;
- Urine pregnancy test (female subjects of childbearing potential). A negative urine pregnancy test must be obtained prior to dosing with the investigational product;
- Assess need for contraception and adherence to applicable lifestyle requirements (Section 4.4). Establish willingness and ability to comply with lifestyle requirements going forward in the study;
- Review eDiary to assess completion;
- Perform drug accountability procedures;

- Reallocate subject to new treatment regimen;
- Dispense oral investigational product to the subject;
- Administer oral investigational product and observe dosing;
- Assess and record any Adverse Events since the last visit.

6.2.8. Visit 9, Day 127/Week 18 (±3 Days)

- Administer PROs including PtGA;
- Obtain pre-dose vital signs including pulse rate, sitting blood pressure, respiratory rate and oral or tympanic temperature (after at least 5 minutes of rest);
- Review PSAAD daily completion (in selected countries), CCI , and Pruritus NRS completion for this visit in the eDiary;
- Review any changes in the subject's concomitant medication and treatments information;
- Check subject understanding of protocol guidance for the use of background topical therapy as described in Section 5.9.1, ensure subject adherence to background topical therapy requirements and re-educate as required;
- Conduct targeted physical examination;
- Conduct clinical evaluations including IGA, SCORAD, EASI and BSA (calculated in the EASI);
- Perform a single 12-lead electrocardiogram (ECG);
- Obtain samples for laboratory testing: serum chemistry, hematology (including coagulation panel), and urinalysis;
- Urine pregnancy test (female subjects of childbearing potential). A negative urine pregnancy test must be obtained prior to dosing with the investigational product;
- Assess need for contraception and adherence to applicable lifestyle requirements (Section 4.4). Establish willingness and ability to comply with lifestyle requirements going forward in the study;
- Review eDiary to assess completion;
- Perform drug accountability procedures;
- Administer oral investigational product and observe dosing;

• Assess and record any Adverse Events since the last visit.

6.2.9. Visit 10, Day 141/Week 20 (±3 Days) End of Treatment or Early Termination Visit

- Administer PROs including PtGA, DLQI, EQ-5D-5L, HADS, and POEM;
- Obtain weight;
- Obtain pre-dose vital signs including pulse rate, sitting blood pressure, respiratory rate and oral or tympanic temperature (after at least 5 minutes of rest);
- Review eDiary Pruritus NRS, CCI , and PSAAD completion (in selected countries) and review eDiary procedures with subject as necessary;
- Review any changes in the subject's prior and concomitant medications and treatment information;
- Check subject understanding of protocol guidance for the use of background topical therapy as described in Section 5.9.1, ensure subject adherence to background topical therapy requirements and re-educate as required;
- Conduct complete physical examination;
- Conduct clinical evaluations including, IGA, SCORAD, EASI and BSA (calculated in the EASI);
- Perform a single 12-lead electrocardiogram (ECG);
- Obtain samples for laboratory testing: serum chemistry, hematology (including coagulation panel), lipid profile (fasting), and urinalysis;

- For China, Republic of Korea, Taiwan, and Japan only: For subjects who had HBV DNA testing at Screening, collect blood sample for repeat HBV DNA testing, as appropriate;
- Urine pregnancy test (female subjects of childbearing potential). A negative urine pregnancy test must be obtained prior to dosing with the investigational product;
- Assess need for contraception and adherence to applicable lifestyle requirements (Section 4.4). Establish willingness and ability to comply with lifestyle requirements going forward in the study;
- Review eDiary to assess completion;

- Perform drug accountability procedures;
- Administer oral investigational product and observe dosing;
- Assess and record any Adverse Events since the last visit;
- Subjects who complete the trial to this visit will be assessed for eligibility for participation in long-term extension study B7451015. Subjects who are not eligible or are not interested are to continue to Visit 11 (see Section 6.3.1).

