HBV DNA testing for China, Japan, Republic of Korea, and Taiwan only ^{aa}	X						X			X	
Tuberculosis Test ^q	X										
Trial Treatment											
Randomization		X									
Oral Drug Dispensing		X			X	X	X	X			
Injectable Drug Dispensing		X		X	X	X	X				
Investigational Product Accountability				X	X	X	X	X	X	X	
Subject Injection Training ^r		X									
Observed Investigational Product Administration ^s		X		X	X	X	X	X	X	X	
Reallocation to new treatment regimens								X			
Review eDiary to assess completion		X	X	X	X	X	X	X	X	X	
Assess eligibility for B7451015 ^t										X	
Clinical Assessments											
Fitzpatrick Skin Type Assessment		X									
Investigator's Global Assessment (IGA)	X	X		X	X	X	X	X	X	X	X
SCORing Atopic Dermatitis (SCORAD)	X	X		X	X	X	X	X	X	X	X

Visit Identifier ^a	Day -28 Screening	Baseline	Call	Day 15 Week 2		Week 8	Day 85 Week 12			Day 141 Week 20 EOT or ET Visit	Day 169 Week 24 (4 Weeks after EOT or ET) EOS, Follow-up Visit
	Visit 1	Visit 2	Visit 3	Visit 4	Visit 5	Visit 6	Visit 7	Visit 8	Visit 9	Visit 10	Visit 11
Visit Window	None	None	±1 Day	±1 Day	±2 Days			±3 Days	±3 Days	±3 Days	±3 Days
Eczema Area and Severity Index (EASI)	X	X		X	X	X	X	X	X	X	X
Body Surface Area (BSA from EASI)	X	X		X	X	X	X	X	X	X	X
C-SSRS ^u	X										
PHQ-8 ^u	X										
Patient-reported Outcomes											
Pruritus Numerical Rating Scale (NRS) ^v	XX	X		X	X	X	X	X	X	X	X
Patient Global Assessment (PtGA)		X		X	X	X	X	X	X	X	X
Dermatology Life Quality Index (DLQI)		X		X			X	X		X	X
Pruritus and Symptoms Assessment for Atopic Dermatitis (PSAAD) ^w	XX	X									X
EQ-5D-5L		X					X	X		X	X
CCI											
Hospital Anxiety and Depression Scale (HADS)		X					X	X		X	
Patient-Oriented Eczema Measure (POEM)		X					X	X		X	
CCI											

Visit Identifier ^a	Day -28 Screening			Day 15 Week 2	Day 29 Week 4	Day 57 Week 8	Day 85 Week 12	Day 113 Week 16		Day 141 Week 20	Day 169 Week 24
		Baseline	Call							Visit	(4 Weeks after EOT or ET)
											EOS, Follow-up Visit
	Visit 1	Visit 2	Visit 3	Visit 4	Visit 5	Visit 6	Visit 7	Visit 8	Visit 9	Visit 10	Visit 11
Visit Window	None	None	±1 Day	±1 Day	±2 Days	±3 Days	±3 Days	±3 Days	±3 Days	±3 Days	±3 Days
Safety											
Serious and non-serious adverse event monitoring	X	X	X	X	X	X	X	X	X	X	X
Contraception Check ^y	X	X	X	X	X	X	X	X	X	X	X
Ensure subject adherence to background topical therapy requirements ^d	X	X	X	X	X	X	X	X	X	X	X
Serum Sample for Baseline Viral Screen ^z		X									

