6.4. Subject Withdrawal

Ongoing safety concern at the time of subject withdrawal from the study:

If a subject has a clinically significant, treatment-emergent, abnormality at the time of withdrawal from the study, the Pfizer Medical Monitor (or designee) should be notified and every effort should be made to arrange follow-up evaluations at appropriate intervals to document the course of the abnormality. All abnormal laboratory events of clinical significance should be followed until the laboratory values have returned to normal or baseline levels or are deemed clinically stable. Follow-up for abnormal laboratory findings and adverse events by the investigator is required until the event or its sequelae resolve or stabilize at a level acceptable to the investigator, and Pfizer concurs with that assessment. Refer to Appendix 4 for Guidelines for Monitoring and Discontinuation.

Withdrawal of consent:

Subjects who request to discontinue receipt of study treatment will remain in the study. If this request occurs at a scheduled visit, an end of treatment visit should be performed and the subject should enter into the follow-up period, with an end of study visit scheduled for 4 weeks after the end of treatment visit. If the request occurs outside of a scheduled visit (eg, via telephone contact) the subject should be scheduled to return to site for an end of treatment visit within one week, and the subject should enter into the follow-up period, with an end of study visit scheduled for 4 weeks after the end of treatment visit.

The only exception to this is when a subject specifically withdraws consent for any further contact with him or her or persons previously authorized by the subject to provide this information. Subjects should notify the investigator in writing of the decision to withdraw consent from future follow-up, whenever possible. The withdrawal of consent should be explained in detail in the medical records by the investigator, as to whether the withdrawal is only from further receipt of investigational product or also from study procedures and/or posttreatment study follow-up, and entered on the appropriate CRF page. In the event that vital status (whether the subject is alive or dead) is being measured, publicly available information should be used to determine vital status only as appropriately directed in accordance with local law.

Lost to follow-up:

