All reasonable efforts must be made to locate subjects to determine and report their ongoing status. This includes follow-up with persons authorized by the subject as noted above. Lost to follow-up is defined by the inability to reach the subject after a minimum of 2 documented phone calls, faxes, or e-mails as well as lack of response by the subject to 1 registered mail letter. All attempts should be documented in the subject's medical records. If it is determined that the subject has died, the site will use locally permissible methods to obtain the date and cause of death. If the investigator's use of a third-party representative to assist in the follow-up portion of the study has been included in the subject's informed consent, then the investigator may use a sponsor-retained third-party representative to assist site staff with obtaining the subject's contact information or other public vital status data necessary to

complete the follow-up portion of the study. The site staff and representative will consult publicly available sources, such as public health registries and databases, in order to obtain updated contact information. If, after all attempts, the subject remains lost to follow-up, then the last-known-alive date as determined by the investigator should be reported and documented in the subject's medical records.

Subjects may withdraw from the study at any time at their own request, or they may be withdrawn at any time at the discretion of the investigator or sponsor for safety (see also the Withdrawal From the Study Due to Adverse Events section) or behavioral reasons, or the inability of the subject to comply with the protocol-required schedule of study visits or procedures at a given study site. Subjects that discontinue study treatment will remain in the study and must have their end of treatment visit within 1 week after their last dose, and will then enter the 4-week follow-up period. See Appendix 4 for Guidelines for Monitoring and Discontinuation.

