• A single HBV DNA test result above the LLQ for a subject requires immediate and permanent discontinuation from treatment, and the Medical Monitor (or designee) must be notified. The subject must be scheduled for an End of Treatment visit/Early Termination visit, enters the end of treatment follow up period, and must be scheduled for an End of Study visit. No further scheduled HBV DNA tests will be required for a subject once a result above the LLQ is established for that subject during any study in the program. Follow up by the investigator is required as detailed in Section 6.4.

Hepatitis C testing: Hepatitis C Antibody (HCV Ab), Hepatitis C Viral RNA (HCV RNA for confirmation of positive HCV Ab result).

Interpretation of Hepatitis C Testing Results:

 HCV Ab positive and HCV RNA positive: Subject is excluded from study participation.

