Appendix 4. Monitoring and Discontinuation Criteria

Monitoring Criteria

The following laboratory abnormalities require prompt retesting:

- Neutrophil counts <1000 neutrophils/mm³; confirmed promptly by repeat testing, ideally within 3-5 days;
- Platelet counts <75,000 platelets/mm³; confirmed promptly by repeat testing, ideally within 3-5 days;
- Any single hemoglobin value <9.0 g/dL or one that drops ≥2 g/dL below baseline; confirmed promptly by repeat testing, ideally within 3-5 days;
- Any single AST and/or ALT elevation >3 times the upper limit of normal regardless
 of accompanying symptoms or the total Bilirubin should prompt repeat testing. This
 should also prompt review of Section 8.4.2; additional investigations must be
 conducted.

Temporary Interruption to Dosing

An investigator can temporarily interrupt dosing for up to a maximum of 14 consecutive days for a subject, for safety reasons or while monitoring abnormal laboratory tests if the investigator judges that this is necessary. In the case of investigational product being withheld, all investigational products that the subject is receiving should be withheld (ie, both oral and injected investigational product, as applicable). The investigator should use their judgement with regard to unscheduled visits/laboratory/clinical assessments required to monitor the subject during this timeframe. If within this timeframe the investigator judges that it is safe to restart dosing, then the subject may restart investigational product. If the investigator judges that it is not safe to restart dosing within this timeframe then the subject must be permanently discontinued from treatment, have an End of Treatment visit and enter the 4-week follow-up period. Doses not taken for the reasons mentioned above do not constitute protocol deviations or medication errors and should not be considered dosing errors, but should be noted in the dosing log with the reason for reduced drug consumption clearly described.

Discontinuation Criteria

Subjects must be permanently discontinued from treatment if they meet any of the following criteria at any point in the study:

- Marked prolongation of the QTcF interval to >500 ms or >60 ms change from screening ECG.
- Serious infection (see definition for Serious Adverse Events in Section 8.2.3).

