- Any bleeding event thought to be associated with a platelet count reduction per the judgement of the investigator (or, if necessary/desired, following discussion with sponsor).
- Adverse event, per judgment of the investigator, requiring discontinuation from treatment (or, if necessary/desired, following discussion with sponsor).
- Any adverse event or laboratory abnormality, that per the investigator's judgement requires withholding of investigational product for >14 days.

NOTE: any initial lab value below must be retested within 48 hours.

- Two sequential platelet counts <50,000/mm³. If the subject has a platelet count <25,000/mm³, investigational product should be temporarily withheld pending the confirmatory retest.
- Two sequential neutrophil counts <500/mm³.
- Two sequential lymphocyte counts <500/mm³.
- Two sequential hemoglobin assessments <8.0 g/dL or <30% from baseline value.
- Any of the following:
 - Two sequential AST or ALT elevations >3 times the upper limit of normal with at least one Total Bilirubin value >2 times the upper limit of normal.
 - Two sequential AST or ALT elevations >3 times the upper limit of normal with an abnormal INR.
 - Two sequential AST or ALT elevations >3 times the upper limit of normal accompanied by symptoms consistent with hepatic injury.
 - Two sequential AST or ALT elevations >5 times the upper limit of normal, regardless of Total Bilirubin or accompanying symptoms.

NOTE:

 Any of the above findings should prompt review of "The Potential Cases of Drug-Induced Liver Injury," Section 8.4.2 for which additional investigations must be conducted. • Two sequential increases in serum creatinine that are >50% over the average of screening and baseline values AND an absolute increase in serum creatinine ≥0.5 mg/dL. At the time of study completion or discontinuation, if a subject should exhibit elevations in serum creatinine ≥33% above the average of screening and baseline values, they will be re-tested every 1 to 2 weeks until the serum creatinine elevation is fully reversed to within 10% of the average of screening and baseline values or has stabilized.

Having met Discontinuation Criteria, the subject must be permanently withdrawn from treatment, have their end of treatment visit, and will then enter the 4-week follow-up period.

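### The shared End of Treatment/Early Termination visit calls for observed oral dosing, with no exception for subjects whose treatment has been permanently stopped

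*Protocol*

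**What the plan says.** Visit 10 in Protocol Section 6.2.9 serves both the Week 20 End of Treatment visit and the Early Termination visit. Its list contains "Administer oral investigational product and observe dosing". The only condition on dosing in that list is a negative urine pregnancy test for women of childbearing potential.

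In the Schedule of Activities, the row "Observed Investigational Product Administration" is marked in the column shared by End of Treatment and Early Termination. Footnote s to that row tells subjects to take product in the clinic rather than at home on visit days. The introduction to Section 6 says in general terms that dosing takes place at the clinic on visit days. None of these places makes an exception for a subject who has stopped treatment.

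Other provisions send stopped subjects to the same visit:

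- Section 7.6.2.1, after an HBV DNA result above the limit of quantification, which requires immediate and permanent discontinuation: "The subject must be scheduled for an End of Treatment visit/Early Termination visit".
- Appendix 4, when a dose hold cannot safely be ended: "not safe to restart dosing within this timeframe then the subject must be permanently discontinued from treatment, have an End of Treatment visit".
- Appendix 4, after the discontinuation criteria: "Having met Discontinuation Criteria, the subject must be permanently withdrawn from treatment, have their end of treatment visit".
- Section 5.2: a subject whose blind is broken is discontinued from the study and goes through the early termination procedures.

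**The concern.** A site working from the Visit 10 list or the Schedule is told to give and observe an oral dose. Some subjects at that visit have been stopped because of a QTcF prolongation, a serious infection, low blood counts, abnormal liver tests, a creatinine rise or detectable HBV DNA. For them the visit list asks for what the stopping rule forbids. What is at stake is a dose given to someone taken off treatment for safety, at any of the approximately 270 planned sites. No estimate or test in the trial is at stake.

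**Working it through.** No figure in the plan bears on this point, so the check is a comparison of texts, followed by a bound on what could happen.

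**1. Status on arrival against the visit list**

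| Route to Visit 10 | Status required before the visit | What Section 6.2.9 then lists |
|---|---|---|
| 7.6.2.1, HBV DNA above the limit (tested only in China, Japan, Republic of Korea and Taiwan) | Immediate, permanent discontinuation | Observed oral dose |
| Appendix 4, hold that cannot safely end within 14 days | Permanent discontinuation | Observed oral dose |
| Appendix 4, discontinuation criteria met | Permanent withdrawal from treatment | Observed oral dose |
| 5.2, blind broken | Discontinued from the study | Early termination procedures, which include the observed oral dose |

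In the first three rows both instructions cannot be followed. The fourth is a further route: Section 5.2 does not restate a treatment stop in the same words, but it calls up the early termination procedures by name.

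**2. Does any text remove the conflict?**

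- The pregnancy condition in Section 6.2.9, read with Section 7.1, blocks dosing of a subject stopped for pregnancy. It does nothing for the other stopping reasons.
- Appendix 4 says of its dose-hold provision: "Doses not taken for the reasons mentioned above do not constitute protocol deviations or medication errors". That protects a site that does not dose on the hold route. It does not cover the discontinuation criteria, HBV DNA or a broken blind.
- Section 6 refers sites to Appendix 4 for monitoring and discontinuation. This makes it likely that the stopping rule wins, but the same introduction also carries the general dosing sentence without an exception.
- The extension-study line in Section 6.2.9 is limited to subjects who complete the trial to that visit. The dosing line has no such limit.

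**3. How large could the effect be?**

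- The Schedule row has marks at Day 1 and Weeks 2, 4, 8, 12, 16, 18 and 20/Early Termination, 8 in all. One of the 8 is affected.
- Oral product is dispensed at Day 1 and Weeks 4, 8, 12 and 16 (5 visits), and not at Visit 10. A dose at Visit 10 could come only from bottles the subject brings back, which Section 5.8 requires at every visit.
- Section 5.5 has subjects take one tablet from each of two bottles daily: 1 × 2 = 2 tablets, one day's dose.
- The documents give no early-termination rate, so the number of subjects affected cannot be calculated.

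**The case against.** The strongest reply is that a specific, mandatory stopping rule governs a generic checklist line. Appendix 4 and Section 7.6.2.1 require discontinuation, and Section 6 points to Appendix 4. A careful site would not dose. This stands, and it is why the point is of low severity. It does not make the written procedure right.

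A second reply is that the Schedule mark means only that whatever dose is due should be observed. The row covers oral and injectable product and is marked at Weeks 16, 18 and 20, although the last injection is planned for Week 14. That is a fair reading of the row and of footnote s. It does not rescue Section 6.2.9, which names oral product and says to administer it.

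Three stronger readings are tempting, and the documents do not support them:

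- A reader might infer that Section 6.4 conflicts as well. It says stopped subjects "must have their end of treatment visit within 1 week after their last dose", and for a request to stop treatment, "If this request occurs at a scheduled visit, an end of treatment visit should be performed". The first sets an outer limit and does not exclude the same day. The second does not say whether that day's dose came before the request. Neither is a clear conflict.
- A reader might contrast Visit 11, which has no dosing line, and infer a deliberate choice at Visit 10. Visit 11 still requires a negative pregnancy test before dosing, at a visit with no dosing. That looks like reused template wording and proves nothing about intent.
- A reader might infer that the protocol intends to re-dose stopped subjects. The mandatory stopping rules contradict that.

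**Conclusion.** The inconsistency is real and should be corrected, at low severity. Section 6.2.9, the Schedule row and the general sentence in Section 6 call for dosing with no exception for stopped subjects. Section 7.6.2.1 and Appendix 4 send subjects to that visit after mandatory permanent discontinuation, and Section 5.2 adds unblinded subjects. The judgement that an actual dose is unlikely assumes that sites let the stopping rules override the visit list. The point has no bearing on efficacy, alpha or power, and the documents support no estimate of how many subjects could be dosed in error.

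**What to change.** State in three places (Section 6.2.9, Schedule footnote s, and the Section 6 sentence on visit-day dosing) that at Visit 10 investigational product is given only to subjects completing Week 20 on treatment, and that it is not given at an Early Termination visit or after permanent discontinuation. Amending Section 6 matters because its sentence is the broadest and would otherwise still point the other way.

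The cost is three wording changes and a note to sites, with no added procedure and no change to any analysis. Nothing else needs editing for this point. The pre-dose wording for vital signs in Section 6.2.9 is already qualified in Schedule footnote f and Section 7.3.1. SAP Appendix 8 repeats the Schedule row but refers to the protocol for procedures, so it does not direct dosing at sites.
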